ICH	International Conference on Harmonisation
IEC	Independent Ethics Committee
IRB	Institutional Review Board
MAC	M. avium complex
NTM	Nontuberculous mycobacteria
PI	Principal Investigator
REDCap	Research Electronic Data Capture
TDNCC	Therapeutics Development Network Coordinating Center
WGS	Whole genome sequencing

PROTOCOL SYNOPSIS

TITLE	Healthcare-associated links in transmission of nontuberculous mycobacteria among patients with cystic fibrosis (HALT NTM)
SPONSOR- INVESTIGATOR	[name] PhD [name]
FUNDING ORGANIZATION	Cystic Fibrosis Foundation (CFF)
NUMBER OF SITES	Up to 20
RATIONALE	
Pulmonary NTM infection is recognized as one of the most challenging infections to treat among CF patients, notable for prolonged treatment courses and often poor response to therapy. Positive cultures for NTM occur in about 20% of children and adults with CF. However, the source of NTM infection, modes of transmission, and exposure risks are poorly understood. It is thought that NTM is primarily acquired from environmental sites including soil and water as well as water supply systems to homes, hospitals, and clinics and from aerosols generated by flowing water from taps, showers, and fountains. Nonetheless, no direct molecular link has been established between environmental NTM and respiratory CF NTM. Healthcare-associated transmission of NTM among CF patients has been suspected and is of growing concern for CF Centers worldwide. Widespread global transmission of NTM, potentially via person-to-person transmission of fomites and aerosols has been reported, but no standardized epidemiologic investigation tool for healthcare-associated NTM acquisition has been published.

STUDY DESIGN	
PART A / Epidemiologic Investigation:
 
The CO-RDP provides a national reference laboratory for CF NTM. NTM respiratory isolates received from CF Care Centers around the U.S. undergo culture, molecular identification, antimicrobial susceptibility, and whole genome sequencing (WGS). Using this approach, the CO-RDP has identified clusters of NTM isolates, defined as highly similar strains at the genomic level, harbored by two or more CF patients who are cared for at the same CF Care Center. These identifications have heightened our concern for potential healthcare-associated NTM acquisition originating from patient-to-patient transmission or a common environmental source within Centers.
 
Using integrated clinical and epidemiological research methods, the HALT NTM retrospective epidemiologic investigation can identify overlaps in source(s) of care between patients with highly similar NTM isolates in a Center. The HALT NTM toolkit facilitates a stepwise process by which individual Centers perform retrospective epidemiologic evaluation of patients identified by the CO-RDP as part of an NTM cluster. HALT NTM is available to the entire CF

	
Foundation Care Network, under a collaborative agreement, to initiate a standardized, independent, confidential, internal NTM outbreak investigation. A control comparison group will also be investigated.
 
PART B / Water Biofilm Collection: Clustered NTM isolates could originate from a shared healthcare water source. Biofilms from healthcare water supplies will be collected and NTM recovered, identified, and sequenced to determine if the respiratory CF NTM strain genotype is similar to those recovered from the healthcare water supply.

PARTICIPANT STUDY DURATION
	
PART A / Epidemiologic Investigation: CF Centers will be eligible for enrollment as NTM clusters are identified by the CO-RDP. The total duration of the study and analysis is 3 years.
 
PART B / Water Biofilm Collection: CF Centers will be eligible for enrollment as NTM clusters are identified by the CO-RDP. The total duration of the study and analysis is 3 years.


PRIMARY OBJECTIVE
	
PART A / Epidemiologic Investigation: Our primary objective is to implement a standardized epidemiologic investigation, via the HALT NTM tool kit, in CF Care Centers identified as having clusters of highly similar NTM isolates. We will assess the origins and prevalence of healthcare associated patient to patient transmission of NTM among different CF Care Centers. We will characterize the source(s) of direct or indirect patient-to-patient transmission of NTM within an individual CF healthcare setting.
 
PART B / Water Biofilm Collection: The primary objective is to determine if NTM strains identified in clusters are related to strains isolated from water biofilm sources in the CF healthcare setting. Because hospital and clinic plumbing sources could pose a risk to CF patients, we aim to perform WGS of NTM isolates from healthcare biofilms obtained from CF Centers with NTM clusters among patients to determine if the biofilm isolates are highly related to the isolates recovered from patients.

SECONDARY OBJECTIVES
	
PART A / Epidemiologic Investigation: The secondary objectives are to:
 
 ▪ Assess degree of proximity of subjects in time and/or space. ▪ Compare the relationship between similarity of strains and degree of proximity of subjects. ▪ Model the relationship between the degree of similarity and strains with the proximity and subject characteristic variables. 
PART B / Water Biofilm Collection:

	
The secondary objectives are to:
 
 ▪ Characterize clinically-relevant NTM isolates and healthcare biofilms. ▪ Describe most common biofilm sources within the healthcare setting harboring clinically relevant NTM isolates.
NUMBER OF PARTICIPANTS	
PART A / Epidemiologic Investigation: Unlimited and based on the number of patients identified in an NTM cluster within an individual CF Care Center (prospectively collected data). Two controls will be identified for every subject within a cluster.
 
PART B / Water Biofilm Collection: N/A

PARTICIPANT SELECTION CRITERIA: Inclusion Criteria	
PART A / Epidemiologic Investigation: Inclusion Criteria:
 
 1. Written informed consent is not required for this retrospective epidemiological study. 2. Diagnosis of CF consistent with the 2017 CFF guidelines. 3. Male or female participant of any age who have a history of NTM species or sub-species collected from expectorated sputum, induced sputum and/or bronchoalveolar lavage and identified by the CO-RDP as falling into a highly-related cluster within a single CF Care Center. 4. Controls subjects are male or female participants of any age who have a history of NTM species or sub-species collected from expectorated sputum, induced sputum and/or bronchoalveolar lavage and identified by the CO-RDP as NOT falling into a highly-related cluster within a single CF Care Center. 
PART B / Water Biofilm Collection: Inclusion Criteria: N/A

PARTICIPANT SELECTION CRITERIA: Exclusion Criteria	
PART A / Epidemiologic Investigation: N/A
 
PART B / Water Biofilm Collection: N/A

CONCOMITANT MEDICATIONS	
Allowed: N/A Prohibited: N/A

PRIMARY ENDPOINT	
PART A / Epidemiologic Investigation: Identification of a shared healthcare-associated source(s) between patients in a CF Care Center.
 
PART B / Water Biofilm Collection:

	Identification of biofilm isolates that are highly related to the isolates recovered from patients.
SECONDARY ENDPOINTS	
PART A / Epidemiologic Investigation: The secondary endpoints are:
 
 ▪ Incidence and prevalence of CF NTM species/subspecies by geographical region. 
PART B/ Water Biofilm Collection: The secondary endpoints are:
 
 ▪ Incidence and prevalence of healthcare-associated water biofilm NTM species/subspecies by geographical region.
EXPLORATORY EVALUATIONS	None
PLANNED INTERIM ANALYSIS	No formal interim analysis involving a data monitoring committee (DMC) is planned.
STATISTICS PRIMARY ANALYSIS PLAN	
PART A / Epidemiologic Investigation: For the primary endpoint, biostatistical analysis of the multicenter data will be completed using both qualitative and quantitative approaches. We will identify a set of variables used to assess degree of proximity of subjects in time and/or space. For example, two subjects with neighboring rooms at a hospital would have close proximity, but proximity would be increased for two subjects at a facility that had longer overlap time, relative to a pair of subjects that had shorter overlap. We will explore creating composite measures of quantitative proximity that incorporate multiple variables. Qualitative measures of proximity, such as location type (testing laboratory, patient room) will also be assessed. Several testing approaches will be used to compare the relationship between similarity of strains and degree of proximity of subjects. In the simplest form, descriptive statistics will be computed for proximity variables, for pairs of subjects who are determined to have similar strains versus those who have dissimilar strains, and multivariate or 2-sample t-tests will be performed to test for differences between these groups. More advanced modeling will be performed to determine the relationship between the degree of similarity in strains with the proximity and subject characteristic variables; multiple linear regression will be used when considering continuous strain similarity, while multiple logistic regression will be used when considering subjects with dichotomized (similar/dissimilar) strains to other subjects.

	
PART B / Water Biofilm Collection:
 
Several testing approaches will be used to compare the relationship between similarity of strains between the clustered patients and environmental isolates. Descriptive statistics will be computed for proximity variables, for pairs of subjects and environmental isolates that are determined to have similar strains versus those who have dissimilar strains, and multivariate or 2-sample t-tests will be performed to test for differences between these groups.


RATIONALE FOR NUMBER OF PARTICIPANTS
	
The CO-RDP provides a national reference laboratory for CF NTM. NTM respiratory isolates received from CF Care Centers around the U.S. undergo culture, molecular identification, antimicrobial susceptibility, and WGS. Using this approach, the CO-RDP has identified clusters of NTM isolates, defined as highly similar strains at the genomic level, harbored by two or more CF patients who are cared for at the same CF Care Center. All CF Centers, found to have clusters of highly-related NTM isolates will be offered enrollment. Subject enrollment is unlimited and based on the number of patients identified in an NTM cluster within an individual CF Care Center (prospectively collected data).

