The CO-RDP comprises multiple coordinated cores which receive, bank, culture, sequence, and analyze NTM clinical isolates from CF clinics around the U.S. Extracted NTM DNA from received samples is sequenced via WGS and analyzed for phylogenetic relatedness. As of January 2019, 123 facilities across the nation have submitted CF NTM isolates that have been sequenced. Phylogenetic data of NTM isolates from CF patients in the U.S. (**Figure 2**), as well as reference and environmental stains worldwide, are being collected in an ongoing fashion by the CO-RDP, and we found that highly similar NTM strains are shared within individual Care Centers (**Figure 3**) as well as between geographically

distant Centers. This work is clinically significant because a shared highly similar strain within a healthcare setting suggests common environmental sources of acquisition or patient- to-patient transmission.⁹

To define relatedness, the CO-RDP has examined the range of single-nucleotide polymorphism (SNP) differences among isolates from different patients compared to longitudinal isolates from the same patients over time to establish an evidence-based SNP threshold that is consistent with a clonal or highly similar strain within each NTM species.^{13,19} As this genomic database expands, thresholds of similarity will be refined through continued acquisition of longitudinal isolates collected from patients. Together, the inter- and intra-patient information defines a threshold to initiate an epidemiologic investigation. As the number of SNPs between strains increases, the likelihood of shared origin decreases. SNP threshold numbers are also dependent on the size of the core genome used to assess similarity. The CO-RDP utilizes WGS and phylogenomic analysis to examine the population structure and diversity of each NTM species and subspecies, and to identify clustered strains that are phylogenetically-related and nearly identical at the core genome level. Using the CO-RDP data driven methodology, a threshold of 15 SNP for *M. abscessus* ssp. *abscessus* (MAB) is stringent, reliable and provides an optimal approach to assess similarity between isolates.^{13,19}

[figure not shown]

Figure 2: CF NTM isolates sequenced by the CO-RDP.

[figure not shown]

Figure 3: CO-RDP identified NTM clusters within 10 CF Care Centers.

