1.2 Overview of Preliminary Studies

When the CO-RDP receives NTM clinical isolates from around the U.S., DNA is sequenced via WGS and analyzed for genetic relatedness at the core genome level. Mycobacterial DNA is sequenced using Illumina MiSeq 2X300 chemistry. Sequence reads are mapped to the appropriate mycobacterial reference genome and compared to find phylogenomic differences at the SNP level. As of January 2019, over 1,000 CF NTM isolates from 631 patients at 92 contributing facilities have *been banked*. To date, 904 CF NTM isolates *have been sequenced from 79 U.S. Care Centers, representing a total of 13 predominant NTM species and subspecies (Figure 2)*. To determine a threshold of genetic similarity for highly similar isolates, pairwise SNP distances in the core genome were calculated between all pairs of “same” (within-patient) or “different” (between-patient) isolates. We observed that 25 or fewer SNPs define background similarity of same-patient isolates for MAB and MMAS. Thus, a conservative threshold of 15 SNPs was chosen to define genetic clusters between patients, representing likely transmission events or shared source acquisition.

Findings: Unpublished data from the CO-RDP of 114 isolates from CF MAB patients across the country demonstrates 26 of 114 (23%) had isolates in highly related clusters. *Twelve of 114 (11%) had isolates in clusters and received care in the same Center. Clusters are occurring among multiple *M. abscessus* subspecies as well as *Mycobacterium avium* complex (MAC) subspecies.*

Preliminary results from one Care Center utilizing the HALT NTM toolkit investigated six clusters of patients with highly similar respiratory NTM isolates, including *M. abscessus* and MAC. The size of the highly related clusters ranged from 2-3 patients. Among the six identified NTM clusters, two clusters occurred with MAB, one with MMAS, *two with *M. avium* (MAV), and one with *M. intracellulare**. No patients within a cluster are related or living together. This is the first description of a MAC cluster.

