4 STUDY DESIGN

4.1 Study Overview

PART A / Epidemiologic Investigation:

This study will retrospectively review and collect data from patients with CF and culture positive for an NTM isolate falling in a highly-related cluster, identified by the CO-RDP, within a single CF Care Center. Two control subjects will be identified by the CO-RDP for every subject falling within a cluster. Retrospective epidemiologic data collection and input into REDCap is detailed (**Appendix 1 and 2**). Up to 20 Care Centers will be offered enrollment.

PART B / Water Biofilm Collection:

This study will also collect and analyze water biofilms from a variety of water sources in the healthcare setting including sink faucets, showerheads, shower hoses, ice machines, drinking fountains, and decorative water features. Environmental sampling instructions are detailed (**Appendix 3**).

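### Controls are not matched on NTM species and the pair analyses are not limited to same-species pairs, so species could confound the proximity comparison

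*Protocol*

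**What the plan says.** **Who is a control.** The Synopsis, inclusion item 4, reads "Controls subjects are male or female participants of any age who have a history of NTM species or sub-species", and its only further restriction is that the person was "identified by the CO-RDP as NOT falling into a highly-related cluster within a single CF Care Center". The Synopsis entry on number of participants adds "Two controls will be identified for every subject within a cluster". Section 4.1 says who chooses: "Two control subjects will be identified by the CO-RDP for every subject falling within a cluster". None of these places mentions the species of the case. Section 6.2 has no control criterion.

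**What similarity means.** Section 1 describes the SNP threshold as one consistent with "a clonal or highly similar strain within each NTM species", and notes that it depends on the size of the core genome used. Section 1.2 describes the measurement: "Sequence reads are mapped to the appropriate mycobacterial reference genome and compared to find phylogenomic differences at the SNP level". The sequenced collection is broad, "representing a total of 13 predominant NTM species and subspecies".

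**What is compared.** The Synopsis analysis plan and Sections 15.1 and 15.3 compare proximity variables between pairs with similar and pairs with dissimilar strains, using t-tests. They also plan linear regression for continuous strain similarity and logistic regression for the dichotomized form. No step is limited to same-species pairs. Species and subspecies appear in Section 15.2 as a baseline characteristic only.

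**Who is analysed.** Section 15.1.1 bases all analyses on the clustered subjects. Read literally, that excludes the controls.

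**The concern.** Every similar pair is a same-species pair, because only such a pair can fall under the threshold. A dissimilar pair may be same-species or cross-species, and nothing in the control criterion or the analysis text separates the two. The exposure contrast, similar versus dissimilar, is therefore tied to species concordance.

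Two things are at stake:

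- **Confounding.** If patients with the same organism tend to be in the same places at the same times for reasons unrelated to transmission, that difference will show up as an association between strain similarity and proximity. The study would read it as a signal of healthcare-associated transmission.
- **An undefined outcome.** The protocol defines no SNP distance between isolates of different species, so the linear regression has no outcome value for such a pair.

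The first can be reduced in the analysis only if enough same-species controls were chosen. A later analysis cannot create controls who were never selected, so the selection rule belongs in the protocol.

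**Working it through.** The protocol states no sample size, power, alpha or overlap rate bearing on this point, so there is no planned figure to reproduce. The check has three parts.

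**1. How common could cross-species pairs be?**

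Section 1.2 gives the taxa of the six clusters at the one preliminary Center: "two clusters occurred with MAB, one with MMAS", plus two with *M. avium* and one with *M. intracellulare*. The number of between-cluster combinations is C(6,2) = 15.

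| Level of distinction | Concordant combinations | Discordant |
|---|---|---|
| Subspecies | 1 (MAB–MAB) + 1 (*M. avium*–*M. avium*) = 2 | 13/15 = 87% |
| Species | C(3,2) = 3 (*M. abscessus*) + 1 (*M. avium*) = 4 | 11/15 = 73% |
| *M. abscessus* versus MAC | 3 + 3 = 6 | 9/15 = 60% |

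Clusters held 2 or 3 patients. Counting patient pairs over all such sizes gives 83–90%, 67–78% and 58–60% respectively. These are between-cluster combinations, not control pairs. They are what the dissimilar group would consist of if Section 15.1.1 were applied literally.

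For controls, the frequencies of the 13 taxa are not in the text. Under random pairing, the cross-taxon share is 1 − Σp². Two assumed extremes:

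- 13 equally common taxa: 1 − 13 × (1/13)² = 0.92.
- One taxon at 80%, twelve sharing 20%: 1 − [0.80² + 12 × (0.20/12)²] = 1 − 0.643 = 0.36.

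**2. What bias follows?**

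Let f be the share of dissimilar pairs that are cross-species. Let p_same and p_cross be the probabilities of overlap in same-species and cross-species pairs when there is no transmission. Then the spurious difference is

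p_same − [(1 − f) p_same + f p_cross] = f (p_same − p_cross).

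| f | p_same − p_cross = 0 | 0.10 | 0.20 |
|---|---|---|---|
| 0 (matched or restricted) | 0 | 0 | 0 |
| 0.36 | 0 | 3.6 points | 7.2 points |
| 0.60 | 0 | 6 points | 12 points |
| 0.87 | 0 | 8.7 points | 17.4 points |

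The bias is zero if either factor is zero.

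**3. What could this do to a test?**

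Illustration with assumed values: 60 similar pairs, 120 control pairs, p_same = 0.50, f = 0.60, two-sided 0.05, pairs treated as independent. The rejection probability with no transmission is Φ[(Δ − 1.96 SE₀)/SE₁], with SE₀ the pooled and SE₁ the unpooled standard error.

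- Overlap unrelated to species (Δ = 0): 5%.
- Cross-species overlap 10 points lower (Δ = 0.06): SE₀ = 0.0788, SE₁ = 0.0789; Φ(−1.20) ≈ 12%.
- Cross-species overlap 20 points lower (Δ = 0.12): SE₀ = 0.0780, SE₁ = 0.0783; Φ(−0.42) ≈ 34%.

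**The case against.** The strongest reply is that control pairs have a stated purpose, which cross-species pairs can serve. The discussion of the preliminary findings in Section 1.2 says control pairs are meant to capture baseline overlap unrelated to transmission. Two patients with different species cannot have shared a strain, so their overlap is background overlap. That stands, as long as overlap does not depend on species. A reader might infer that the comparison measures species rather than strain sharing, or that cross-species pairs are uninformative. The documents do not support either reading: the compared variable is proximity.

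Second, controls are selected as non-clustered, so a same-species control is also dissimilar to its case by selection. That is ordinary in a case-control comparison. The difference that remains is that a same-species control could in principle have been similar and a cross-species control could not.

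Third, a reader might infer that species cannot be adjusted for. That is also too strong. Species is recorded, and Section 15.1 allows subject characteristics in the models. If some same-species dissimilar pairs exist, a same-species term can be estimated when proximity is the response. In the logistic model for similarity that term predicts cross-species pairs perfectly, so they cease to inform the proximity effect, which amounts to restricting the analysis. Covariates and restrictions may be set out in the SAP, which is not at hand. None of this helps if few same-species controls were chosen.

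Fourth, no place in the protocol says that admissions, scheduling or overlap differ by NTM species. This also stands: the mechanism is possible but undocumented.

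**Conclusion.** The point holds as a gap in control selection and in the definition of the pair analyses. The text fixes no species rule for controls and no restriction to same-species pairs, while defining similarity only within a species. It follows that species could confound the proximity comparison and that continuous similarity is undefined for cross-species pairs.

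The size is uncertain. It is tempting to conclude that most control pairs will be cross-species, but the protocol does not give the taxon mix of controls, does not say whether control pairs join a control to a case or to another control, and leaves the choice to a laboratory that knows the species. The 36–92% range rests on assumed distributions, and 13 of 15 describes one Center's clusters. The false-positive rates of 12% and 34% need an assumed overlap difference of 10 or 20 points between same-species and cross-species pairs; with no such difference there is no bias. The change is nevertheless worth making because it is cheap and must be in place before controls are chosen.

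**What to change.** - **Synopsis item 4 and Section 4.1:** have the CO-RDP choose controls of the same species (same subspecies where defined) as the case, where available. Where fewer than two exist, take controls of another species for the descriptive estimate of baseline overlap only.
- **Section 15.3 and the matching text in the Synopsis and Section 15.1:** run the t-tests and the linear and logistic models on same-species pairs (same-subspecies where defined). Report cross-species pairs separately, as descriptive background overlap.
- **Section 15.1.1:** reconcile it with the Synopsis and Section 4.1, so that the analysis set says whether controls are included and in which analyses.

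The cost is one criterion and a few sentences of analysis text; the CO-RDP already knows the species when it picks controls. The downside is that some cases, with rarer taxa or at small Centers, will have fewer than two matched controls. Keeping the other controls for description limits that loss.

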Testing for water biofilm sources in the CF healthcare setting: NTM are known to colonize municipal water systems and have been identified in healthcare facilities.²⁷⁻²⁹ NTM are found in free flowing water as well as biofilms on water supply system pipes and both have been implicated in nosocomial outbreaks of infection.³⁰ Modes of acquisition and transmission of NTM among CF patients remains unclear. A multicenter prevalence study of NTM in 2003 did not implicate nosocomial transmission among CF patients, and molecular analysis at that time revealed almost all patients had unique NTM strains.³¹ A more recent study described a biphasic nosocomial outbreak of MAB linked to hospital tap water.³² The authors attributed the first phase of the outbreak of respiratory MAB to routine care practices using hospital tap water with exposure to the aerodigestive tract in high-risk patients. The second phase outbreak occurred among cardiac surgery patients with invasive MAB infections and was attributed to contaminated heater-cooler units of cardiopulmonary bypass machines. Others have implicated inhalation of aerosolized NTM via showerheads as a possible source of acquisition of infection.³³ A recent study demonstrated that showerheads receiving water from municipal water treatment plants **harbor clinically-relevant NTM**.³⁴ On a more global level, Bryant *et al.* reported widespread dominant circulating NTM clones.¹¹ This worldwide distribution could be explained by **prevalent environmental genotypes**. Further environmental evaluation of healthcare environments is essential to understanding healthcare-associated environmental risk factors in **acquisition of NTM infection**.

Biofilms are the preferred samples for isolation of NTM in water systems of all types because the hydrophobic NTM cells preferentially adhere to pipe surfaces where they form biofilms, thus ensuring their persistence. Average colony counts/cm² of premise plumbing biofilm samples is between 1,000-15,000 CFU/cm², whereas water (suspended) densities are between 10-100 CFU/mL.³⁵ Thus, the sensitivity of NTM detection is **orders of magnitude higher for biofilm** compared to water samples. With advanced molecular analysis and better understanding of previous NTM nosocomial outbreaks, the CO-RDP findings of highly related NTM clusters among CF patients within the same CF Care Centers **raises concern for nosocomial**

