15.1.1 Data Sets Analyzed

All analyses will be based on the group of subjects that are identified by the CO-RDP as having NTM isolates, defined as highly similar strains at the genomic level, harbored by two or more patients within a single Care Center.

152 Demographic and Baseline Characteristics

The following baseline demographic and clinical characteristics will be reported: age, gender, race, ethnicity, zip code, and NTM sub/species.

153 Analysis of Primary Endpoint

PART A / Epidemiologic Investigation:

The primary endpoint will characterize the origins and prevalence of healthcare-associated patient-to-patient transmission of NTM among different CF Care Centers. We will further characterize the source(s) of direct or indirect transmission of NTM within an individual CF healthcare setting. We will identify a set of variables used to assess degree of proximity of subjects in time and/or space. For example, two subjects with neighboring rooms at a hospital would have close proximity, but proximity would be increased for two subjects at a facility that had longer overlap time, relative to a pair of subjects that had shorter overlap. We will explore creating composite measures of quantitative proximity that incorporate multiple variables. Qualitative measures of proximity, such as location type (testing laboratory, patient room) will also be assessed. Several testing approaches will be used to compare the relationship between similarity of strains and degree of proximity of subjects. In the simplest form, descriptive statistics will be computed for proximity variables, for pairs of subjects who are determined to have similar strains versus those who have dissimilar strains, and multivariate or 2-sample t-tests will be performed to test for differences between these groups. More advanced modeling will be performed to determine the relationship between the degree of similarity in strains with the proximity and subject characteristic variables; multiple linear regression will be used when considering continuous strain similarity, while multiple logistic regression will be used when considering subjects with dichotomized (similar/dissimilar) strains to other subjects.

PART B / Water Biofilm Collection:

The primary endpoint will characterize clinically-relevant NTM found in water biofilms within CF healthcare settings and determine if the biofilm isolates are highly related to isolates recovered from patients.

154 Analysis of Secondary Endpoints

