PART A / Epidemiologic Investigation:

The secondary endpoints will characterize CF Center adherence to the CF IP&C guidelines as well as characterize points of patient overlap. Basic summaries of points of potential transmission overlap will be provided.

PART B / Water Biofilm Collection:

The incidence and prevalence of NTM species and subspecies within healthcare water biofilms will be characterized. Comparisons of NTM biofilm isolates and highly related patient isolates will be provided.

155 Interim Analysis

No formal interim analysis involving a data monitoring committee (DMC) is planned. However, annual reports summarizing key variables related to site enrollment and adherence to protocol

will be generated. These reports will help guide protocol revisions. Details of the planned analysis for these annual reports can be found in the Statistical Analysis Plan (SAP).

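### Part B names no off-Center reference for its biofilm isolates, so a match shows relatedness but cannot, in the stated analysis, support a Center-specific water source.

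*Protocol*

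**What the plan says.** - **Where biofilms come from.** Synopsis, Primary Objective, Part B: sequencing is planned on isolates from "healthcare biofilms obtained from CF Centers with NTM clusters among patients". No Center without a cluster is sampled.
- **What they are compared with.** Synopsis, Statistics Primary Analysis Plan, Part B: the aim is to "compare the relationship between similarity of strains between the clustered patients and environmental isolates". Proximity variables are then summarised and tested "for pairs of subjects and environmental isolates that are determined to have similar strains versus those who have dissimilar strains".
- **Analysis set.** Section 15.1.1: "All analyses will be based on the group of subjects that are identified by the CO-RDP as having NTM isolates", with those isolates defined as highly similar strains carried by at least two patients of one Center.
- **Section 15.4, Part B.** "Comparisons of NTM biofilm isolates and highly related patient isolates will be provided".
- **Controls.** Two per clustered subject, listed in the synopsis under Part A; the Part B entry is N/A. In the discussion of preliminary results in section 1.2, the control pairs are meant to capture overlap that has nothing to do with transmission.
- **Strains across Centers.** Section 1: "highly similar NTM strains are shared within individual Care Centers", and the sentence goes on to say that they are also shared between Centers far apart. Section 2, on dominant circulating clones: "This worldwide distribution could be explained by" environmental genotypes that are simply common.
- **Preliminary data.** Section 1.2: the unpublished *M. abscessus* ssp. *abscessus* (MAB) series "demonstrates 26 of 114 (23%) had isolates in highly related clusters"; 12 of 114 (11%) were in clusters and had care in the same Center.

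**The concern.** A genetic match between a clustered patient and a swab from that patient's Center has at least two explanations. The Center's water may have been the source, or the strain may be widespread and turn up in many places. The two can be separated only by asking how often the same biofilm isolates match patients who never attended that Center. The stated Part B analysis does not ask this.

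The protocol accepts the same reasoning for Part A, where control pairs supply a baseline for overlap. Part B has no counterpart. Choosing Centers because two or more patients share a strain may also favour common strains, for which the question matters most.

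At stake is the inference that motivates Part B. The synopsis Study Design raises a shared healthcare water source as a possible origin of clusters. Section 1.2 wants a common healthcare source ruled out when patients had no contact. Section 2 closes on the risk of nosocomial acquisition.

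**Working it through.** The protocol gives no sample size, power or match rate for Part B, so there is no Part B figure to reproduce. The check has three parts.

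**1. Is an off-Center reference named anywhere for Part B?**

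| Place | What it fixes | Off-Center reference |
|---|---|---|
| Synopsis, Primary Objective | biofilms from Centers with clusters | none |
| Synopsis, Statistics | clustered patients against environmental isolates | none |
| 15.1.1 | all analyses on clustered subjects | points the other way |
| 15.3 | whether biofilm isolates are highly related to patient isolates | none |
| 15.4 | biofilm isolates against highly related patient isolates | none |

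Section 1 says that the CO-RDP collects phylogenetic data on U.S. CF isolates and on reference and environmental strains worldwide. Section 1.2 counts 904 sequenced isolates from 79 Care Centers. No Part B text says that biofilm isolates will be set against them.

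**2. Is high similarity Center-specific in the protocol's own data?** Inputs from section 1.2, MAB patients, with exact (Clopper-Pearson) intervals:

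- In any highly related cluster: 26/114 = 22.8% (95% CI 15.5 to 31.6); the stated 23% is reproduced.
- In a cluster and cared for in the same Center: 12/114 = 10.5% (5.6 to 17.7); the stated 11% is reproduced.
- Clustered but not counted as same-Center: 26 − 12 = 14, and 14/26 = 53.8% (33.4 to 73.4).

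So patients with highly similar strains often do not share a Center. The 14 is obtained by subtraction and is not itself stated. It concerns patient-to-patient similarity and says nothing direct about how often biofilms match patients.

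**3. Why the background rate matters (illustration only).** Let s be the chance of a match when the Center's water is the source, and c the chance of a match when it is not. With even prior odds, the probability that a match reflects a Center source is s/(s + c). The protocol gives neither quantity; s = 0.8 and the range of c are assumptions.

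| c | s/(s + c) |
|---|---|
| 0.02 | 0.8/0.82 = 0.98 |
| 0.10 | 0.8/0.90 = 0.89 |
| 0.30 | 0.8/1.10 = 0.73 |
| 0.50 | 0.8/1.30 = 0.62 |

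The same match is near-conclusive or weak depending on c, and the stated comparison does not estimate c.

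**The case against.** **Part B asks about relatedness, not source.** This stands. The objectives and the synopsis endpoint ask whether biofilm and patient strains are related, and a match answers that whether or not the clone is widespread. Section 1 also requires evidence of exposure, besides a genetic match, before transmission is accepted. A reader might infer that every match would be reported as a positive result biased against hospital plumbing. The documents do not support that: nowhere do they say that a match alone will be declared the Center's source.

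**Cross-Center comparison is not excluded.** Also true. The synopsis endpoint and sections 5.2 and 15.3 speak of patients' isolates without limiting them to clustered patients. The similar-versus-dissimilar pairs could cross Centers, and section 15.1 refers to multicenter data. The body's Part B endpoint in section 5.1 includes commonly occurring environmental genotypes. So the limitation lies in the analysis as written, not in the data. But no text states a reference comparison, and section 15.1.1 points away from one.

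**A SAP could hold the detail.** Which database isolates to use could sit there. The sampling frame, the analysis set and the comparison, however, are fixed in the protocol, and section 15.5 cites the SAP only for the annual reports.

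**Coincidental matches may be rare.** Possibly. Section 1 says that no direct molecular link between environmental and respiratory CF isolates has been established, so c could be close to zero. That is a reason to estimate it, not to assume it.

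**Conclusion.** The point holds as a limit on what Part B can conclude. As written, a biofilm match satisfies the relatedness endpoint but cannot support a Center-specific water source, because no background match rate is planned and the protocol itself says that similar strains cross Centers.

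Its size can be shown only indirectly. Among clustered MAB patients, 14 of 26 (53.8%, 95% CI 33.4 to 73.4) were not counted as same-Center. This rests on unpublished data for one subspecies and on a subtraction. It would be tempting to read 54% as the share of biofilm matches that would be coincidental, or to derive an expected number of false matches across the enrolled Centers. The documents give no biofilm match rate, so neither figure can be had from them.

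**What to change.** In the synopsis Part B analysis and in sections 15.3 and 15.4, with section 15.1.1 amended to allow it:

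1. Besides the comparison with clustered patients, compare each biofilm isolate, within species and at the species-specific SNP threshold, with CO-RDP patient isolates from other Centers and with the reference and environmental strains already held.
2. Report own-Center and off-Center match rates side by side.
3. Label a match to a multi-Center strain as non-specific for source, meaning that it neither confirms nor excludes a local source. Do not discard it: a Center's water may truly be the source of a common clone, and dropping such matches would bias the result the other way.
4. Unclustered patients at the same Center may be reported descriptively but should not serve as the background rate, since they too may have acquired their strain from that Center's water. The protocol also does not say that controls come from the same Center.

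The cost is extra computation on genomes already held and a few lines of protocol text. No new patients or samples are needed. Some matches will support a weaker conclusion than they otherwise might.
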